A phase 1, single-center, double-blind, placebo-controlled clinical trial to evaluate the safety, tolerability, pharmacokinetics and preliminary efficacy of multiple oral administrations of TNP-2092 Capsules in asymptomatic healthy subjects with Helicobacter pylori infection

Protocol

Protocol No.: TNP-2092-03

Approval Date: 25 July 2017

ClinicalTrials.gov ID: NCT06190340

Protocol of Study TNP-2092-03

Name of Sponsor Company: TenNor Therapeutics (Suzhou) Limited.	Individual Study Table Referring to Part of the Dossier Volume: Page:	(For National Authority Use Only)
Name of Finished Product: TNP-2092 capsules		
Name of Active Ingredient: TNP-2092		
Title of study: A phase 1, single-center, double-blind, placebo-controlled clinical trial to evaluate the safety, tolerability, pharmacokinetics and preliminary efficacy of multiple oral administrations of TNP-2092 Capsules in asymptomatic healthy subjects with Helicobacter pylori infection		
Investigator: [name], The First Hospital of Jilin University		
Study center: The study will be conducted in a single center in China.		
Publication (Reference): None.		
Clinical Phase: 1		

Objectives
 
 1) To evaluate the safety and tolerability of multiple oral dose-escalation administrations of TNP-2092 Capsules in asymptomatic healthy subjects with Helicobacter pylori infection. 2) To evaluate the pharmacokinetic characteristics of multiple oral dose-escalation administrations of TNP-2092 Capsules. 3) To explore the preliminary efficacy of TNP-2092 Capsules in eradicating Helicobacter pylori through the ¹⁴C urea breath test (UBT). 		

Methodology
 
This study is a single-center, randomized, double-blind, placebo-controlled, dose-ascending multiple-dose-administration study. The aim of this study is to evaluate the safety, tolerability, and pharmacokinetic profile of TNP-2092 Capsules in asymptomatic healthy subjects with Helicobacter pylori infection, and to explore the preliminary efficacy of TNP-2092 Capsules in eradicating Helicobacter pylori.
		

In this study, three dose groups of 100 mg, 300 mg and 600 mg will be set up. The drug will be taken twice a day for 14 consecutive days, and last dose on the morning of Day 15. Fifteen subjects in each of the 100 mg and 300 mg dose groups will be randomized at a ratio of 4:1, with 12 subjects receiving the investigational product and 3 receiving placebo. Ten subjects in the 600 mg dose group will be randomized at a ratio of 4:1, with 8 subjects receiving the investigational product and 2 subjects receiving placebo.
		

During the trial, blood samples will be collected from the subjects at the specified time points for pharmacokinetic analysis. In the 300 mg group, urine and stool samples will be collected from 7 subjects who are first enrolled in the group for metabolic transformation study.
		

Plasma sample:
 
 • Blood samples are collected at different time points. Day 1: before the first administration (within 60 minutes), 0.5, 1, 2, 3, 4, 6, 8, 10 and 12 hours after administration; Day 15: before administration (within 60 minutes), 0.5, 1, 2, 3, 4, 6, 8, 10, 12, 16, 24, 36, 48 and 72 hours after administration; Days 2-14: before the first administration every day (within 60 minutes), the trough concentration is measured to monitor the complete pharmacokinetic changes. • Urine sample (300 mg BID dose group - for 7 subjects who are first enrolled in the group only): • Urine samples are collected before administration and 0-6 hours, 6-12 hours, 12-24 hours, 24-48 hours and 48-72 hours after administration on Day 15 for metabolic transformation study. 		

Name of Sponsor Company: TenNor Therapeutics (Suzhou) Limited.	Individual Study Table Referring to Part of the Dossier Volume: Page:	(For National Authority Use Only)
Name of Finished Product: TNP-2092 capsules		
Name of Active Ingredient: TNP-2092		

 • Stool sample (300 mg BID dose group - for 7 subjects who were first enrolled in the group only): • Stool samples are collected within 72 hours after administration on Day 15 for metabolic transformation study. 
All of the subjects will be followed up by the ¹⁴C-urea breath test (UBT) to evaluate the eradication of Helicobacter pylori.
		

Number of subjects
 
It is planned to enroll 40 subjects, eight subjects will be administrated with placebo, and 32 subjects will be administrated with TNP-2092 capsules (12 subjects each with 100 mg or 300 mg, and 8 subjects with 600 mg).
		

Diagnosis and main criteria for inclusion
 
Each subject will be required to meet all of the following criteria to be eligible for study enrollment:
 
 1) Those who are fully informed of and understand this study and have signed the Informed Consent Form. 2) Those who are willing to follow and able to complete all the trial procedures. 3) Female subjects of childbearing potential must agree to abstinence or take effective contraceptive measures during the trial and at least 70 days (10 weeks) after administration. 4) Male subjects must agree to abstinence or use condoms as a contraceptive measure during the trial and at least 70 days (10 weeks) after administration. 5) Sex: male or female. 6) Age: 18-45 years, including 18 and 45 years. 7) BMI: 19.0-26.0 kg/m², including 19.0 and 26.0 kg/m². 8) Those who do not smoke, or have smoked less than 5 cigarettes per day within 3 months before screening; those who do not drink alcohol, or have drunk less than 14 units of alcohol per week (1 unit of alcohol = 360 mL of beer or 45 mL of spirits with 40% alcohol content or 150 mL of wine) within 6 months before screening; those who have not smoked or drunk alcohol within 48 hours before admission to the study site. 9) Subjects whose clinical laboratory test results are within the normal range or whose test results are abnormal but judged by the investigator to be of no clinical insignificance. 10) Those with a positive ¹⁴C urea breath test (UBT) result. 
Subjects meeting any of the following criteria will be ineligible for study enrollment:
 
 1) Those with an allergic constitution, a history of allergic diseases or a history of drug allergy. 2) Those with a history of alcohol or drug abuse in the past 10 years. 3) Those who have donated blood within 3 months before enrollment. 4) Those with regular use of any prescription/over-the-counter drugs, including vitamins, minerals, nutritional supplements or herbs, within 2 weeks before enrollment and during the study period. 5) Those who have taken any drug that changes the activity of liver enzymes 28 days before taking the investigational product or during the study. 6) Those who have participated in any clinical trials within 3 months before enrollment. 7) Those with a history of eradication of Helicobacter pylori. 		

Name of Sponsor Company: TenNor Therapeutics (Suzhou) Limited.	Individual Study Table Referring to Part of the Dossier Volume: Page:	(For National Authority Use Only)
Name of Finished Product: TNP-2092 capsules		
Name of Active Ingredient: TNP-2092		

8) Those who are suffering or have suffered from digestive tract diseases, including digestive tract ulcer, etc.
 
9) Those with symptoms or past medical history of cardiovascular, respiratory, urinary, neurological, blood, immune, endocrine system diseases or tumor, mental illness, or any situation which, in the opinion of the investigator, may threaten the safety of the subjects or affect the correctness of the trial results.
 
10) Those whose blood pressure remains above 140/90 mmHg after retest.
 
11) Pregnant or lactating women.
 
12) Those who are HIV positive, syphilis positive, hepatitis B surface antigen positive, hepatitis C antibody positive.
 
13) Those who have had beverages or foods containing methylxanthine (coffee, tea, coke, chocolate, and energy drinks), grapefruit (fruit juice) and alcohol within 48 hours (2 days) before the clinical study.
 
14) Other circumstances deemed by the investigator to be unsuitable for the subject to participate in this study.
		

Investigational product, dose and regimen of administration
 
Investigational product: TNP-2092 capsules.
 
Dose and regimen of administration: Subjects will be administrated TNP-2092 capsules orally twice daily at the dose of 100 mg, 300 mg, and 600 mg in the fed state for consecutive 14 days and the last dose in the fed state on the morning of Day 15.
		

Duration of treatment
 
Approximately up to 63 days (from signing ICF to the end of the study).
		

Reference treatment, dose and regimen of administration
 
Placebo: TNP-2092 placebo capsules.
 
Dose and regimen of administration: the same regimen as that of TNP-2092 capsules.
		

Criteria for evaluation
 
Pharmacokinetics
 
T_{max}, C_{max}, $t_{1/2}$, $AUC_{0-\infty}$, AUC_{0-last}, AUC_{0-tau}, V_d and CL, $T_{max,ss}$, $C_{max,ss}$, $C_{min,ss}$, $C_{avg,ss}$, $t_{1/2,ss}$, $AUC_{0-last,ss}$, $AUC_{0-tau,ss}$, $AUC_{0-\infty,ss}$, V_{ss}, CL_{ss}, accumulation index, fluctuation index, trough concentration.
		

Safety
 
incidence of AEs, the relationship between the drug and AEs, severity of AEs, physical examination, clinical laboratory tests (hematology, blood chemistry, coagulation, and urine test), vital signs (blood pressure, pulse and body temperature) and 12-lead ECG.
		

Efficacy
 
^{14}C UBT.
		

Statistical methods
 
SAS 9.4 will be used for the statistical analysis.
		

Sample size simulation
		

Name of Sponsor Company: TenNor Therapeutics (Suzhou) Limited.	Individual Study Table Referring to Part of the Dossier Volume: Page:	(For National Authority Use Only)
Name of Finished Product: TNP-2092 capsules		
Name of Active Ingredient: TNP-2092		

This study is an early phase exploratory clinical trial, the sample size is not based on statistical hypothesis test, but based on the assessment of safety, PK, and preliminary efficacy in line with similar trials. The sample size of 15 patients in both of the 100 mg and 300 mg dose groups, and 10 patients in the 600 mg group are also appropriate for the purpose of the exploration of the PK profile, safety, and efficacy of TNP-2092 capsules.
		

Population for analyses
 
 • Full Analysis Set (FAS): all the subjects who have been randomized into groups. • Safety Analysis Set (SS): all the subjects who have been randomized into groups and received at least one dose of study drug. • PK Concentration Analysis Set (PKCS): all the subjects who have been randomized into groups, received at least one dose of study drug, and have at least one evaluable blood drug concentration. • PK Parameter Analysis Set (PKPS): all subjects who have been randomized into groups, have received at least one dose of study drug, and have at least one evaluable pharmacokinetic parameter. 		

Interim analysis
 
No interim analysis is planned.
		

PK analysis
 
Pharmacokinetic analysis will be based on the PKPS. Pharmacokinetic concentration and parameters will be subjected to descriptive analysis by dose group. The mean and individual drug-time curves will be shown graphically. Numbers will include individual values and mean values. In addition, individual and mean dose standardization parameters will be plotted against the dose to evaluate whether there are any obvious trends.
		

Safety and tolerability analysis
 
It will be based on the SS. Physical examination results and changes, laboratory test results and changes, vital signs results and changes, as well as ECG results and changes will be descriptive analyzed by dose group and planned time point. The abnormal results of these examinations will also be listed. Adverse events (AEs) will be coded using the Medical Dictionary for Regulatory Activities (MedDRA) and summarized by treatment group and dose according to the system organ class (SOC) and preferred terms (PTs). In addition, serious adverse events (SAEs) and AEs leading to dropout and death will be listed separately.
		

Efficacy analysis
 
The preliminary Helicobacter Pylori eradication efficacy will be analyzed based on FAS. The number and percentage of subjects with ^{14}C UBT negative at the follow-up visit will be listed by dose group. Fisher's exact test was used for comparison of percentages between groups (if infeasible for data reasons, summarize only). For all measurements, the baseline values and changes from baseline will be summarized by dose group and visit. Changes from baseline will be compared between groups by visit using analysis of covariance model, with baseline value as covariate and treatment group as fixed effect factors. Missing values will be imputed using last observation carry forward (LOCF). Sensitivity analysis will be performed using mixed model for repeated measures (MMRM), with baseline value and treatment group as fixed effect factors. An unstructured covariance matrix will be preferred in the model, if not fitted, other suitable covariance matrix would be used.
		

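### The plan pre-specifies no estimate or interval for how exposure scales over 100, 300 and 600 mg, although the planned data allow one

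*Combined protocol and SAP*

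**What the plan says.** The second objective is "To evaluate the pharmacokinetic characteristics of multiple oral dose-escalation administrations of TNP-2092 Capsules". Under Methodology, "three dose groups of 100 mg, 300 mg and 600 mg will be set up", and the Number of subjects section gives "32 subjects will be administrated with TNP-2092 capsules (12 subjects each with 100 mg or 300 mg, and 8 subjects with 600 mg".

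The paragraph headed PK analysis (Statistical methods) is the whole PK plan. It opens with "Pharmacokinetic analysis will be based on the PKPS" and then specifies:

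- descriptive summaries of concentrations and parameters by dose group;
- individual and mean concentration-time curves;
- individual and mean dose-standardised parameters, "plotted against the dose to evaluate whether there are any obvious trends".

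The Criteria for evaluation already list Cmax, AUC0-tau, Cmax,ss, AUC0-tau,ss, CL and CLss. No section gives a model, slope, ratio, interval or definition of a trend for the relation between dose and exposure. On size, the plan says "the sample size is not based on statistical hypothesis test".

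**The concern.** Plotting dose-standardised parameters against dose has one purpose, which is to see whether exposure rises in step with dose. The plan therefore asks the question itself, although it never uses the term dose proportionality. The cross-dose method it names is inspection of a plot. What counts as an obvious trend is not defined, so two readers of the same plot may disagree, and neither can say how large a departure the data leave open.

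At stake is the usefulness of one main PK result of a dose-ascending study: how exposure behaves over a six-fold dose range, and how precisely that is known. The exploratory label does not by itself explain the gap. The Efficacy analysis section, equally exploratory, names Fisher's exact test, an analysis of covariance and a mixed model for repeated measures.

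**Working it through.** **Plan's own figures.** The only figures here that can be reproduced are the counts. Group sizes are 15 + 15 + 10 = 40. At 4:1 these give 12 + 12 + 8 = 32 active and 3 + 3 + 2 = 8 placebo, as stated. The plan gives no PK precision, margin or variability to reproduce.

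**Model.** ln(parameter) = a + b·ln(dose), one value per active subject; b = 1 means proportional.

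**Inputs from the documents.** Doses 100, 300 and 600 mg with n = 12, 12 and 8.

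**Assumptions.** Log-normal parameters with the same between-subject CV at each dose; CV from 30 to 60%; all 32 evaluable.

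**Step 1, spread of ln(dose).** The values are 4.605, 5.704 and 6.397, with weighted mean 5.465. Then Sxx = 12(0.739) + 12(0.057) + 8(0.868) = 16.50, with 32 − 2 = 30 df.

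**Step 2, precision.** σ = √ln(1 + CV²); SE(b) = σ/√16.50; the 90% half-width is 1.697·SE. For a true slope of 0.75, the chance that the 90% CI excludes 1 comes from the non-central t distribution with non-centrality −0.25/SE.

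| Assumed CV | σ | SE(b) | 90% half-width | 600 v 100 mg dose-normalised ratio, 90% CI if b is estimated as 1 | P(CI excludes 1), true b = 0.75 |
|---|---|---|---|---|---|
| 30% | 0.294 | 0.072 | 0.123 | 0.80–1.25 | 96% |
| 40% | 0.385 | 0.095 | 0.161 | 0.75–1.33 | 82% |
| 50% | 0.472 | 0.116 | 0.197 | 0.70–1.42 | 68% |
| 60% | 0.555 | 0.137 | 0.232 | 0.66–1.51 | 56% |

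The ratio limits are 6 raised to ± the half-width. A slope of 0.75 means that dose-normalised exposure at 600 mg is 6^(−0.25) = 0.64 of that at 100 mg. In simulation (20,000 data sets per scenario) the 90% CI covered the true slope in about 90% of cases.

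**Step 3, fewer evaluable subjects.** With an assumed 10, 10 and 6, the half-width becomes 0.14 at CV 30% and 0.22 at CV 50%.

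**Step 4, can it establish proportionality?** A 0.80–1.25 range over a six-fold dose span corresponds to slopes within 1 ± ln(1.25)/ln(6) = 1 ± 0.125. At CV 30% the half-width of 0.123 already uses almost all of that, so the CI fits inside only if the estimate falls almost exactly at 1. (This range is only a yardstick; the plan sets no margin.)

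**Step 5, does a straight line on the log scale suffice?** Two noiseless patterns with n = 12, 12 and 8:

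- *Proportional from 100 to 300 mg, then flat to 600 mg.* The fitted slope is 0.69. It implies a 600 v 100 mg ratio of 6^(−0.31) = 0.57 when the true ratio is 0.50, and a loss between 100 and 300 mg that does not exist.
- *Dose-normalised exposure 40% higher at 300 mg only.* The fitted slope is 1.06, which looks near-proportional.

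The planned plot would show both shapes and the slope alone would not. Ratios for adjacent doses would also show them. For a dose-normalised geometric mean ratio, the 90% CI is the estimate multiplied or divided by exp(1.699·σ·√(1/n₁ + 1/n₂)), with σ pooled on 29 df. At CV 30% that factor is 1.23 for 300 v 100 mg and 1.26 for 600 v 300 mg. At CV 50% it is 1.39 and 1.44.

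**The case against.** The strongest reply is that the plan fits its stated purpose. The trial is exploratory, its size rests on no hypothesis, the objective is to characterise PK, and the plan promises no conclusion on proportionality. Escalation depends on safety and tolerability (Study Flowchart, note 12), so no decision described in the documents turns on PK scaling. The regression could also be run later from the individual values. This stands, and it limits the point to an improvement in estimation. It does not remove the point, because an estimate with an interval needs no hypothesis, margin or larger sample, and specifying it beforehand prevents a choice of method after the data are seen.

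A reader might go further in four ways that the documents or the arithmetic do not support:

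- *That scaling is judged only by eye and the trial can say nothing about it in numbers.* Summaries by dose are planned, and CL and CLss relate dose to exposure, so their summaries allow a crude numerical comparison. What is missing is a pre-specified estimate with an interval.
- *That no visible trend will be taken as proof of proportionality.* The plan states no such inference.
- *That the model would clearly detect a slope of 0.75.* At CV 60% the chance is only 56%.
- *That the interval should override the plot.* Step 5 of the working shows why this is unsound with three doses.

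**Conclusion.** The point holds as a gap in estimation: a cheap improvement worth making, not an error that invalidates the trial. The plan summarises and plots exposure by dose but attaches no estimate or uncertainty to the dose-exposure relation. The planned data would give a slope to within about ±0.12 to ±0.23 (90% CI), which is informative about sizeable departures when variability is low to moderate. These figures depend on the assumed CVs of 30 to 60%, a common log-scale variance and 32 evaluable subjects. Higher variability or losses would widen them. The result is unlikely to establish proportionality, and the interval would make that limit visible where a plot does not.

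**What to change.** Keep the planned summaries and plots. Add to the PK analysis section, for TNP-2092 recipients in the PKPS:

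1. The power model for Cmax and AUC0-tau on Day 1 and for Cmax,ss and AUC0-tau,ss on Day 15, reporting b with its 90% CI and the implied 600 v 100 mg dose-normalised ratio.
2. Dose-normalised geometric mean ratios with 90% CIs for 300 v 100 mg and 600 v 300 mg, as a check on log-linearity.
3. A statement that these results are estimation with no pass/fail claim, and are interpreted together with the plots.

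The cost is a few lines of text, four regressions and the matching ratios. No extra subjects or samples are needed. The downside is a little more analysis work and an interval that will probably be too wide to establish proportionality.

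### Does the plan need to define its analysis groups so that the eight placebo subjects are not split by cohort or mixed into the doses?

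*Combined protocol and SAP*

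**What the plan says.** The Methodology section sets up three dose levels and randomizes within each. For the two lower doses it reads: "dose groups will be randomized at a ratio of 4:1, with 12 subjects receiving the investigational product and 3 receiving placebo". The top dose has 8 on TNP-2092 and 2 on placebo. The sample size paragraph under Statistical methods uses the term in the same way: "The sample size of 15 patients in both of the 100 mg and 300 mg dose groups". In both places a dose group is a cohort with its placebo subjects included.

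The Number of subjects section counts by treatment instead: "eight subjects will be administrated with placebo, and 32 subjects will be administrated with TNP-2092 capsules". A separate section of the synopsis names placebo capsules as the reference treatment.

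The analysis sections vary the wording:

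- **PK analysis:** "Pharmacokinetic concentration and parameters will be subjected to descriptive analysis by dose group".
- **Safety, measurements:** "vital signs results and changes, as well as ECG results and changes will be descriptive analyzed by dose group and planned time point".
- **Safety, adverse events:** "summarized by treatment group and dose according to the system organ class".
- **Efficacy, breath test:** the number and percentage "UBT negative at the follow-up visit will be listed by dose group".
- **Efficacy, test of proportions:** Fisher's "exact test was used for comparison of percentages between groups", with a fallback to summary only.
- **Efficacy, ANCOVA and MMRM:** treatment group is a fixed effect.

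The levels of these groupings are not listed, and the Statistical methods text does not mention placebo.

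**The concern.** Taken literally, the cohort meaning of *dose group* carries over into the efficacy and safety tables. Each dose's eradication rate and mean laboratory, vital-sign or ECG change would then be one-fifth placebo. A second possible reading compares active with placebo inside each cohort, which leaves two or three controls per comparison. A third uses three doses and one pooled placebo group of eight.

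The same data look quite different under these readings. The breath test is the only efficacy measure, and safety is the first objective. If the text truly left the choice open, the grouping could be settled once the results were known.

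**Working it through.** **1. The plan's own figures.** At 4:1, 15 × 4/5 = 12 and 15 × 1/5 = 3 in each of two cohorts; 10 × 4/5 = 8 and 10 × 1/5 = 2. The totals are 12 + 12 + 8 = 32 active and 3 + 3 + 2 = 8 placebo, 40 in all. This agrees with the Number of subjects section.

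**2. Placebo mixed into each dose.** Because 12/15 = 8/10 = 0.8, the displayed rate is 0.8 × active rate + 0.2 × placebo rate. With an active rate of 50% and placebo 0% (both assumed), it is 0.8 × 50% = 40%. Complete eradication on active with none on placebo would show as 12/15 = 8/10 = 80%.

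**3. Placebo split by cohort or pooled.** The exact two-sided 95% upper limit for zero events in n is 1 − 0.025^(1/n). The standard error of an active-minus-placebo mean difference, in SD units, is √(1/n₁ + 1/n₂).

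| Placebo used | Upper limit for zero events | SE, 12 active | SE, 8 active |
|---|---|---|---|
| Own cohort | 71% (0/3), 84% (0/2) | 0.645 (12 v 3) | 0.791 (8 v 2) |
| Pooled | 37% (0/8) | 0.456 (12 v 8) | 0.500 (8 v 8) |

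Pooling reduces the standard error by 1 − 0.456/0.645 = 29% and 1 − 0.500/0.791 = 37%.

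Fisher's test on illustrative counts (two-sided):

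| Active responders | Own-cohort placebo | Pooled placebo |
|---|---|---|
| 6/12 | 0/3: p=0.229 | 0/8: p=0.042 |
| 5/8 | 0/2: p=0.444 | 0/8: p=0.026 |

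With no placebo responders, p≤0.05 needs 9/12 or 8/8 against own-cohort placebo, but only 6/12 or 5/8 against pooled placebo. The 0.05 level is an assumption, since the plan states none.

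**4. Which reading the text supports.**

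- *Mixed.* This is remote. The title calls the trial placebo-controlled and the synopsis names a reference treatment. The adverse event tables are by treatment group as well as dose, and the models are fitted on treatment group. In the PK analysis *dose group* can sensibly mean only subjects given TNP-2092, so the term is not tied to the cohort meaning.
- *Split by cohort.* Randomization within each dose makes this possible, but no analysis sentence calls for it, and it leaves two or three controls.
- *Pooled.* The Number of subjects section treats the eight placebo subjects as one set beside 12, 12 and 8. Treatment group as a model factor fits four levels. It also fits two levels, 32 against 8, and that reading pools placebo too.

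**5. Effect under the natural reading.** With pooled placebo, each dose is summarized on its own 12, 12 or 8 subjects and placebo on 8. The dilution in step 2 and the loss of precision in step 3 do not arise.

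**The case for a change.** The best case for a change is that it costs only wording. The plan names Fisher's test, an ANCOVA and an MMRM, and any planned test should say which groups it compares. The Statistical methods text itself uses *dose group* for the cohort with placebo. Pooling is plausible but nowhere stated, and a nominal p-value can move from 0.04 to 0.23 with the choice. The comparisons are unlisted as well: dose against dose, one overall test, or all active against placebo are not excluded.

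Much of this stands as description. The groups and contrasts are not listed, and the arithmetic is correct. Pooling also has a price: footnote 12 of the Study Flowchart has the dose groups run in sequence, so pooled placebo is not fully concurrent with every dose.

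The stakes do not stand at the size claimed. The large differences arise only under readings that the rest of the plan makes unlikely or that an analyst would not choose with two or three controls. The sample size is stated not to rest on a hypothesis test, efficacy is the third and exploratory objective, and Fisher's test may be dropped for a plain summary, so crossing 0.05 decides nothing in this plan. Nor do the documents say when the groups are fixed, so a choice made after seeing results is conjecture.

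**Conclusion.** No change is called for. The wording is loose and the detail is missing, but the plan states no rule shown to be wrong, and its enrolment figures reconcile exactly. A competent analyst would present TNP-2092 100 mg (12), 300 mg (12), 600 mg (8) and placebo (8), and spelling this out would change no number under that reading.

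If placebo were instead split by cohort, the cost would be precision: an upper limit of 71% or 84% in place of 37% for a zero placebo rate, and standard errors of 0.645 and 0.791 SD in place of 0.456 and 0.500. In an exploratory trial of 40 subjects that would be visible from the group sizes and would not mislead. Adverse events, already summarized by treatment group and dose, are less exposed.

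This conclusion assumes that pooled placebo is what the sponsor intends. The reference treatment and the single count of eight support that, although no sentence confirms it. The p-values rest on illustrative counts with no placebo responders, and the 0.05 level is assumed.

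### Unrestricted LOCF fills a missing follow-up breath test with the Day 16 result in the by-visit ANCOVA, and the plan does not say whether it also reaches the eradication percentage

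*Combined protocol and SAP*

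**What the plan says.** All the relevant analysis text is in the synopsis, under Statistical methods, Efficacy analysis.

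- **Analysis set.** The "eradication efficacy will be analyzed based on FAS", and the set is defined under Population for analyses: "Full Analysis Set (FAS): all the subjects who have been randomized into groups". A subject without a follow-up UBT therefore stays in the denominator.
- **Binary endpoint.** The number and percentage of subjects with "UBT negative at the follow-up visit will be listed by dose group", with Fisher's exact test between groups where feasible.
- **Continuous analysis.** "For all measurements, the baseline values and changes from baseline will be summarized by dose group and visit". Then: "Changes from baseline will be compared between groups by visit using analysis of covariance model".
- **Missing data.** The next sentence is "Missing values will be imputed using last observation carry forward (LOCF". It has no qualifier.
- **Sensitivity analysis.** "Sensitivity analysis will be performed using mixed model for repeated measures (MMRM), with baseline value and treatment group as fixed effect factors". No visit or treatment-by-visit term is named.

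The Appendix 1 Study Flowchart schedules UBT at screening, on Day 16 before breakfast (footnote 3) and at follow-up. The last dose is given on Day 15, 30 minutes after the start of breakfast (footnote 13). Every subject is positive at entry under inclusion criterion 10: "Those with a positive ¹⁴C urea breath test (UBT) result".

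**The concern.** LOCF is harmless only when the last observation is a fair stand-in for the missing one. Here the only post-baseline value available to carry is an end-of-treatment test. The plan itself places eradication at follow-up, and a Day 16 result says nothing about what happens after Day 16. If some subjects on TNP-2092 are negative on Day 16 but not eradicated, carrying that result makes the follow-up comparison look better than it is. If Day 16 is missing too, LOCF carries the positive screening value, a change of zero, which works against the drug.

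The second difficulty is scope. The LOCF sentence does not say whether it governs the eradication percentage and the Fisher test. Two statisticians following the plan could report different rates from the same data, and with 8 or 12 active subjects per dose a single subject is visible.

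**Working it through.** **Denominators.** From the synopsis: (12 + 3) + (12 + 3) + (8 + 2) = 40, of whom 12 + 12 + 8 = 32 are active and 3 + 3 + 2 = 8 are placebo. This agrees with the planned 40. There is no power calculation to reproduce.

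**What LOCF carries to follow-up.**

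| Day 16 UBT | Follow-up UBT | Value used at follow-up |
|---|---|---|
| observed | observed | follow-up |
| observed | missing | Day 16 |
| missing | missing | screening (positive) |

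For subjects who took the Day 15 dose, the Day 16 test precedes breakfast and the dose followed the start of the previous day's breakfast, so the gap is under about 24 hours. It is longer for those who stopped early. I rely only on follow-up coming after Day 16, as the order of the flowchart columns shows. The window printed in that column heading (Day 4 - 49) may be damaged text, and I give it no weight.

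**Follow-up ANCOVA.** Each carried Day 16 value shifts the raw arm mean by 1/12 or 1/8 of that subject's unobserved change from Day 16 to follow-up. That change may be zero, and the documents give no figure for it.

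**Eradication percentage, broad reading only.** One carried negative in a non-eradicated subject adds 1/12 = 8.3 points (100 or 300 mg) or 1/8 = 12.5 points (600 mg). For the expected bias, let:

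- m = number with follow-up missing and Day 16 observed
- n = active arm size
- p = true eradication probability
- s = chance that a non-eradicated subject is negative on Day 16
- t = chance that an eradicated subject is negative on Day 16

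If missingness is unrelated to eradication, each such subject is counted negative with probability pt + (1 - p)s, where the truth is p. Hence

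bias = m[(1 - p)s - p(1 - t)]/n.

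The documents give none of m, p, s or t, so all values below are assumed. Percentage points for m = 1:

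| p | t | n = 12: s = 0 / 0.5 / 0.9 | n = 8: s = 0 / 0.5 / 0.9 |
|---|---|---|---|
| 0.3 | 1 | 0 / +2.92 / +5.25 | 0 / +4.38 / +7.88 |
| 0.3 | 0.8 | -0.50 / +2.42 / +4.75 | -0.75 / +3.63 / +7.13 |
| 0.7 | 1 | 0 / +1.25 / +2.25 | 0 / +1.88 / +3.38 |
| 0.7 | 0.8 | -1.17 / +0.08 / +1.08 | -1.75 / +0.13 / +1.63 |

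Example: p = 0.7, s = 0.5, t = 0.8, n = 12 gives (0.15 - 0.14)/12 = 0.08 points. The t = 1 rows are upper values. Two missing subjects double every entry.

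**Fisher's test, for orientation.** Placebo is assumed all positive; the plan states neither pooling of placebo nor an alpha. One carried negative changes the two-sided p-value as follows:

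| Step | Pooled placebo 0/8 | Same-cohort placebo |
|---|---|---|
| 5/12 to 6/12 | 0.055 to 0.042 | 0.51 to 0.23 (0/3) |
| 4/8 to 5/8 | 0.077 to 0.026 | 0.467 to 0.444 (0/2) |

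Against 0/8 these are the only single-subject steps that cross 0.05. Against same-cohort placebo neither does.

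**The case against.** The strongest reply has four parts.

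1. The binary endpoint is tied to the follow-up visit on all randomized subjects, and the LOCF sentence sits between the ANCOVA and the MMRM. Its natural scope is the continuous change score. A Day 16 negative is not a follow-up negative, so a missing follow-up already counts as not eradicated. **This stands as the more natural reading.** It removes the 8.3 and 12.5 points, but the plan does not state it, and it leaves the ANCOVA untouched.
2. Nothing suggests that follow-up will often be missing. Subjects stay on site until Day 18, and flowchart footnote 1 asks early terminators to complete the later visits. **This stands as a limit on size.** It sets no imputation rule, and follow-up is the one UBT after discharge.
3. An MMRM, which carries nothing forward, is already planned, and unstated visit terms may be synopsis brevity. **This stands in part.** As written, with baseline and treatment only, the model gives one treatment effect over both visits and does not isolate follow-up. It also does not cover the binary endpoint.
4. Counting missing as not eradicated has a bias of its own. **This is correct**; the fix gives its size.

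A reader might go further and infer that the plan counts Day 16 negatives as eradications, that the reported rates will be inflated, or that a significant result could be manufactured. The documents do not support any of these. The first rests on the less natural reading. The second needs missing follow-up tests and false Day 16 negatives, neither of which is documented. The third needs a threshold, and no stated decision depends on one: the sample size rests on no hypothesis test, and the plan allows summary only.

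**Conclusion.** The point holds for the continuous analysis. Followed as written, the plan puts an end-of-treatment value into the follow-up ANCOVA whenever follow-up is missing and Day 16 was observed, provided a numeric UBT is analysed, as a change from baseline implies. That value does not measure the plan's own follow-up endpoint. Confidence in this is high. The size is unknown and may be zero.

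For the eradication percentage and Fisher's test, the finding is an ambiguity. The 8.3 and 12.5 points per subject apply only under the broad reading and only to a non-eradicated subject. The expected bias may be positive, zero or slightly negative, depending on m, p, s and t. It is zero if no follow-up UBT is missing.

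Severity is low: efficacy is the third, exploratory objective of a 40-subject phase 1 trial. It is still worth correcting, because the rule as stated can give a wrong follow-up result and is cheap to change.

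**What to change.** 1. State that the Day 16 UBT is not carried forward to the follow-up visit.
2. State that in the FAS percentage and Fisher's test a missing follow-up UBT counts as not eradicated, and show an observed-case table beside it.
3. For the continuous value, take the follow-up contrast from the planned MMRM, with visit and treatment-by-visit terms written in, in place of the LOCF ANCOVA. Day 16 changes need no new table, because they are already summarized by visit.

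The cost is text and programming only, with no new data or visits. With two post-baseline tests, an unstructured covariance has 3 parameters.

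There are downsides. Counting missing as not eradicated is biased low by mp/n. Over p = 10% to 70% with one missing, that is 0.8 to 5.8 points (n = 12) or 1.25 to 8.75 points (n = 8). At t = 1 it exceeds the carry-forward bias in absolute size when p > s/(1 + s), for example above 33% at s = 50%. It is proposed as a conservative bound, not as an unbiased estimate, and the observed-case table shows how much it matters. The MMRM assumes data are missing at random, and a subject with neither post-baseline UBT contributes no outcome to it.
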